12.3.4 Safety analysis

For safety analysis, laboratory parameters, all AEs and all SAEs will be analyzed via descriptive statistical methods in the safety population. The safety analysis includes calculation of frequencies and rates of complications and serious adverse events together with corresponding 95%-confidence intervals. In addition, tolerability and dosing will be described by numbers of patients in whom treatment was given as planned, delayed or permanently stopped.

Further details of the analysis will be specified in the statistical analysis plan (SAP) which will be finalized before database closure. All analyses will be done using R version 3.6.3 or higher.

12.3.5 Homogeneity of the intervention groups

The homogeneity of the treatment groups will be described by comparison of the demographic data and the baseline values.

12.4 Interim analysis

A group-sequential design with interim analysis containing decision boundaries without sample size recalculation will be performed after availability of the results for the primary endpoint for a total of 49 randomized patients (i.e., 50% of the sample size).

The following type I error rates, decision boundaries for the interim and the final analysis are specified:

- Global one-sided type I error rate: $\alpha = 0.025$
- Boundary for the one-sided p-value for accepting the null-hypothesis within the interim analysis: $\alpha_0 = 0.2879$ (according to an O'Brien-Fleming type beta-spending approach). This rule is considered as a non-binding stopping rule for futility.
- One-sided local type I error rate for testing the null-hypothesis within the interim analysis: $\alpha_1 = 0.0015$ (according to an O'Brien-Fleming type alpha-spending approach)
- Boundary for the one-sided p-value for testing the null-hypothesis within the final analysis: $\alpha_2 = 0.0235$ (according to an O'Brien-Fleming type alpha-spending approach)

The trial will only be continued as planned after the interim analysis, if for the one-sided p-value p_1 of the interim analysis $p_1 \in]0.0015, 0.2879[$ holds true. Furthermore, descriptive progression-free-survival and overall survival will be analyzed at the interim analysis using Kaplan-Meier-Curves. The 1-year and 2-year survival rates as well as the median survival rate will be provided alongside two-sided 95%- confidence intervals.

In case the trial is prematurely stopped due to efficacy or futility, patients who are still under observation but were not yet included in the interim analysis will not be followed up as planned.

It should be noted that the interim analysis will likely take place after the total number of 120 patients have been enrolled. While in such a case, it is not possible to reduce the total number of enrolled patients, the follow-up time of the trial might be reduced, thus allowing to save resources and costs.

Results of the interim analysis will be presented to the Data Safety and Monitoring Board (DSMB) who will advise the Steering Committee of the trial to either terminate or to continue the trial.

Detailed procedures of the interim analysis will be specified in a separate interim Statistical Analyses Plan (SAP), which will be finalized before interim database lock.

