For a fixed sample size design, the sample size required to achieve a power of $1 - \beta$ of 80% for the one-sided negative binomial regression at a significance level of $\alpha = 0.025$ in conventional and experimental group and a randomization allocation ratio of 1 as well as the above-mentioned assumptions, amounts to $2 * 46 = 92$. It can be expected that including covariates of prognostic importance in the negative binomial regression model as defined for the confirmatory analysis (see section 13.3) will increase the power as compared to no included covariates.

As the individual results for the primary endpoint are collected within 24 months, there is a possibility of some patients not surviving the observation period, becoming lost to follow-up or withdrawing their informed consent. If a patient discontinues from the study prematurely without having a full observation time (e.g. due to death, loss to follow, or withdrawal of informed consent) but was observed for at least one year after randomization, the primary outcome variable will be set to the number of lesions observed until the last available follow-up visit. If a patient has a follow-up less than one year after randomization, the primary endpoint will be set to missing. In order to take this potential loss of information into account, a premature death rate of 8% and a drop-out rate of 10% (loss to follow or withdrawal of informed consent) after 12 months is assumed. Thus, an overall “drop-out” rate of 18% after 12 months is assumed, and therefore the total sample size required for a fixed design amounts to $n = 92 + 22 = 114$ patients (57 per group).

A group-sequential design with interim analysis allowing to prematurely stop the trial for efficacy or futility, using O’Brien-Fleming-type alpha and beta spending functions, is

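### The final-analysis p-value boundary of 0.0235 is only the alpha left after the interim; the O'Brien-Fleming-type spending boundary it is said to be is 0.0245

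*Protocol*

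**What the plan says.** Protocol Section 12.4 (Interim analysis) sets out the whole decision rule:

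- overall level: "Global one-sided type I error rate: $\alpha = 0.025";
- timing: one interim "for a total of 49 randomized patients (i.e., 50% of the sample size");
- interim efficacy: "One-sided local type I error rate for testing the null-hypothesis within the interim analysis: $\alpha_1 = 0.0015";
- interim futility: "Boundary for the one-sided p-value for accepting the null-hypothesis within the interim analysis: $\alpha_0 = 0.2879", with the comment "This rule is considered as a non-binding stopping rule for futility";
- final analysis: "Boundary for the one-sided p-value for testing the null-hypothesis within the final analysis: $\alpha_2 = 0.0235".

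Both efficacy figures are attributed to an O'Brien-Fleming-type alpha-spending approach, and the futility figure to beta spending of the same type. Section 11 (Sample Size) describes the design in the same way. It gives 92 patients for the fixed design at 80% power and 98 (49 per group) for the group-sequential design before drop-out. No other place in the protocol gives a different final boundary.

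**The concern.** The interim and final figures add up exactly to 0.025. That is how the alpha increments of a spending function behave, but not how nominal p-value boundaries behave. The interim data are part of the final data, so some of the trials that would cross the final boundary have already crossed at the interim. The final boundary can therefore be less strict than the remaining alpha and still keep the total at 0.025.

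The wording leaves no room to read the figure as an increment. The interim figure is called a local type I error rate, while the final one is called a boundary for the p-value. Anyone applying Section 12.4 would compare the final p-value with 0.0235, and that comparison decides the primary hypothesis.

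**Working it through.** **Inputs** (Sections 11 and 12.4): one-sided α = 0.025; power 80%, so β = 0.20; information fraction t = 49/98 = 0.5; O'Brien-Fleming-type spending for α and β; non-binding futility; fixed-design total 92.

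**1. Interim alpha.** The spending function is α(t) = 2·[1 − Φ(z₁₋α/₂ / √t)]. With z = 2.2414 and t = 0.5 it gives 0.001525, or c₁ = 2.963. The stated 0.0015 reproduces.

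**2. Final boundary.** Under the null, (Z₁, Z₂) is bivariate normal with correlation √0.5. Futility is left out because it is non-binding. Solve P(Z₁ > c₁ or Z₂ > c₂) = 0.025:

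- c₂ = 1.9686, one-sided p = 0.02450 (0.02451 if the interim alpha is rounded to 0.0015).
- The remaining alpha is 0.025 − 0.001525 = 0.02347, which rounds to the stated 0.0235.

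**3. Overall level under each final boundary** (interim 0.0015):

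| Final boundary | Overall one-sided level |
|---|---|
| 0.0235 | 0.0240 |
| 0.0245 | 0.0250 |

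**4. Which boundary belongs to the protocol's other figures?** Beta spent at the interim is 2·[1 − Φ(z₀.₉₀ / √0.5)] = 0.0699. The drift m is the expected final Z that gives 80% power with this beta spending. The futility bound on the Z scale is Φ⁻¹(0.0699) + m·√0.5, and the inflation factor is (m / 2.8016)², where 2.8016 = z₀.₉₇₅ + z₀.₈₀.

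| Final boundary | Drift m | Futility p | Inflation | 92 × inflation |
|---|---|---|---|---|
| 0.0245 | 2.879 | 0.2879 | 1.056 | 97.2 |
| 0.0235 | 2.896 | 0.2837 | 1.069 | 98.3 |

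The stated futility bound of 0.2879 matches 0.0245 to four decimals and does not match 0.0235. The stated total of 98 also follows from 97.2 rounded up, whereas 98.3 would exceed it. The sample-size check is the weaker of the two because 92 is itself rounded.

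**5. Could another design give 0.0235 together with 0.0015?**

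- Classical O'Brien-Fleming constants give 0.0026 and 0.0240.
- Treating futility as binding gives a final boundary of 0.0265.
- Of the information fractions tried from 0.4 to 0.8, only 0.5 gives an interim alpha of 0.0015.

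Only the subtraction 0.025 − 0.0015 returns 0.0235.

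**6. Power at 49 per group.** Take rates of 0.86 and 0.18 (Section 11) and 1/0.2597 as the variance dispersion, the reading that gives 46.3 per group for the fixed design, close to the stated 46. With the futility bound obeyed, power is 79.7% with 0.0235 and 80.1% with 0.0245. At the exact design drift of 2.879 the pair is 79.6% and 80.0%.

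**The case against.** The case on the other side accepts the arithmetic and disputes its weight.

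- **The error is conservative.** A test of size 0.0240 is a valid test at level 0.025, so no false-positive claim is at risk. This stands. The point is that the rule is not the method named, and that it gives away part of the stated level.
- **The pair 0.0015 and 0.0235 is safe whatever the correlation**, because the two add up to 0.025. A fixed pair of 0.0015 and 0.0245 is not: the level would be 0.02503 at t = 0.48, 0.02510 at t = 0.445 and 0.02517 at t = 0.408 (49 of 120). The interim is triggered by a patient count, and up to 120 patients are enrolled, so t may well differ from 0.5. This also stands, although the excess is at most 0.0002. It is a reason to tie the boundary to the spending function at the observed information, not to keep a mislabelled figure.
- **The power statement is conditional.** If the non-binding futility rule is ignored, power with 0.0235 is 81.6%. The effect assumptions are also open: taking 0.2597 directly as the variance dispersion gives about 98% fixed-design power at 49 per group, and the synopsis states the effect differently from Section 11. The absolute power values should therefore be read with care. The loss of about 0.4 points holds under the assumptions that reproduce the protocol's own sample size.
- **The verdict changes only in a window 0.001 wide.** True. The planned totals of 98 and 120 are not affected.

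Deferral to the statistical analysis plan does not answer the point. The protocol fixes the number itself, and a plan using 0.0245 would contradict it.

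**Conclusion.** The concern holds. The figure of 0.0235 is the alpha increment, printed as a p-value boundary. Under the stated method, at information fraction 0.5 and with non-binding futility, the boundary is z = 1.969, p = 0.0245, and the protocol's futility bound confirms that its other figures come from that design.

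The consequence is modest: an overall level of 0.0240 instead of 0.0250, about 0.4 points of power, and a wrong verdict for a final one-sided p between 0.0235 and 0.0245. Type I error is not inflated. The power figures assume rates of 0.86 and 0.18, the dispersion reading that reproduces the fixed sample size, and adherence to the futility rule. The correction should be made because the number decides the confirmatory test.

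**What to change.** In Section 12.4, replace the final boundary of 0.0235 by 0.0245 (z = 1.969) at information fraction 0.5. If 0.0235 is kept, label it as the alpha spent at the final analysis and give 0.0245 beside it as the p-value boundary.

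Add that, if the interim does not fall at exactly half the information, the boundaries are recomputed from the spending function at the observed information fraction. With that sentence the overall level stays at 0.025.

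Carry the same figure into the statistical analysis plan. Make the change before the interim analysis, since raising the threshold once data have been seen would look like a relaxation after the fact. The cost is one number and one sentence; the sample size does not change.

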12.4.1 Randomisation

Screened and eligible patients will be included into the trial once the study has been initiated. The patients will be randomized with the help of the web-based software randomizer.at (provided by the Institute for Medical Informatics, Statistics and Documentation; Medical University of Graz; <https://www.randomizer.at>). Block randomization stratified by center will be performed to ensure approximately equal sample sizes within the treatment groups.

13 Ethical, legal and administrative aspects

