5.1 Treatment planning

For treatment planning, patients will be immobilized using an individually manufactured head mask. Both CT as well as contrast enhanced MR-imaging will be performed for optimal target definition. CT slice thickness should be 1 mm. Treatment planning MRI should be performed with 3T not earlier than 4 weeks prior to radiotherapy. Minimum required sequences are:

- T1 MPRAGE with and without contrast enhancement, slice thickness ~ 1mm
- 3D FLAIR / dark fluid TIRM, slice thickness ~ 1mm

Treatment planning in the control arm is performed with the available treatment planning system at each participating center (e.g. Siemens Syngo TPS, Raysearch Raystation) using a fixed RBE of 1.1. Each plan should aim for a dose distribution as homogenous and as conformal as possible. The number and directions of beams are adapted to the patient anatomy. Single beam plans must be avoided whenever possible. The optimization strategy in the conventional treatment planning arm is not determined by the protocol. In principle both Single Beam Optimization/Single Field Uniform Dose or IMPT could be used. Model-based NTCP is calculated after plan approval, however, no further adjustments are to be made to the approved treatment plan.

Re-planning in the experimental arm is performed with Raysearch Raystation, a commercially available treatment planning software with CE certification as medical medical product, using identical beam directions and normal tissue constraints as the initial treatment plan. Compared to the initial treatment plan, the following optimization objectives are modified and added, respectively:

1. the optimization objectives that control the maximum dose in the target volume employ a variable, LETd-dependent model for RBE that allows us to include the RBE-variations predicted by the NTCP model
2. the periventricular volume, defined as the volume closer than 4 mm to the ventricular wall, is included into the optimization with a constraint on its Equivalent Uniform Dose (EUD) and with the variable RBE model described above. Thereby, the combined effect of the RBE variation and increased sensitivity of the periventricular volume, as predicted by the NTCP model, is included.

The effectiveness of the re-planning is verified by a second NTCP computation.

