6.1 Overview

Treatment schedule	baseline visit	weekly during RT	end of RT	FU 1 6 weeks post RT	FU 2 3 months post RT	FU 3 6 months post RT	FU 4 9 months post RT	FU 5 12 months post RT	FU 6 15 months post RT	FU 7 18 months post RT	FU 8 21 months post RT	FU 9 24 months post RT
Informed consent	✓											
Inclusion / exclusion criteria	✓											
Demographic information	✓											
Anamnesis/ clinical examination	✓			✓	✓	✓	✓	✓	✓	✓	✓	✓
randomization	✓											
AEs und SAEs	✓	✓	✓	✓	✓	✓	✓	✓	✓	✓	✓	✓
Symptoms/toxicity	✓	✓	✓	✓	✓	✓	✓	✓	✓	✓	✓	✓
MRI	✓			✓	✓	✓	✓	✓	✓	✓	✓	✓
QLQ-C30 & QLQ-BN20	✓		✓			✓		✓				✓
PRO-CTCAE	✓	✓	✓	✓	✓	✓	✓	✓	✓	✓	✓	✓
(Cognitive assessment)	✓		✓			✓		✓				✓

The number of trial visits and the extent of their examinations is equivalent to standard care. Trial related additional expense is a result of the neurocognitive testing. The MoCA test is designed to take less than 15 min. Completing the PRO-CTCAE form takes less than 5 min. Additional time is needed for completing the quality of life questionnaires which takes approx. additional 20 min per visit. In total, the additional time expense for the patient sums up to 40 min on five trial visits and 5 min at the remaining visits.

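### Randomisation is scheduled at the baseline visit, and nothing requires contours and the initial plan to be locked before the arm is known

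*Protocol*

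**What the plan says.** **Timing of allocation.** The visit table in section 6.1, repeated as the flowchart in the synopsis, has columns beginning "Treatment schedule baseline visit weekly during RT end of RT". The row "randomization" is ticked once, at the baseline visit, alongside consent and the eligibility check. No column covers contouring, plan approval or re-planning. Section 12.4.1 says "Screened and eligible patients will be included into the trial once the study has been initiated" and "Block randomization stratified by center will be performed to ensure approximately equal sample sizes within the treatment groups". Neither sentence relates allocation to planning.

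**Planning.** Under section 5.1, "The number and directions of beams are adapted to the patient anatomy" and "The optimization strategy in the conventional treatment planning arm is not determined by the protocol". The control plan is frozen after approval: model-based NTCP is then computed, but "no further adjustments are to be made to the approved treatment plan". The experimental re-plan is made "using identical beam directions and normal tissue constraints as the initial treatment plan".

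**Masking and endpoint.** Section 3.1 describes the trial as observer blind. Section 7.1.1 has two radiologists read the scans, and counts new enhancement that lies outside the GTV and inside the 80% isodose.

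**The concern.** The intervention is itself a planning step. The design appears meant to isolate it: the target and dose rules are common to both arms (section 1.3), and the re-plan keeps the beam geometry of the initial plan. That isolation works only if initial plans in the two arms are made in the same way, and knowledge of the arm is the obvious threat to this. A planner who knows that a plan will be re-optimised may choose beams that suit re-optimisation. A planner who knows that it will not be may take more care, or less.

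At stake is what the primary result can be attributed to. A difference in lesion counts could partly reflect different initial contours or beam choices rather than the model-aided objectives. Blinded image reading cannot remove such a difference, because it arises before any follow-up scan. The primary model in section 12.3.2 adjusts for treatment, prescribed dose and centre, none of which captures beam choice or contour.

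**Working it through.** The point rests on the order of steps, so it is checked by setting the sections side by side.

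1. **Is randomisation placed relative to planning?** Both visit tables put it at the baseline visit, and the next column is weekly visits during RT. This shows that randomisation comes before RT and nothing finer. Section 5.1 dates the planning MRI only relative to the start of radiotherapy. Section 12.4.1 is silent. The order of contouring, initial plan and allocation is therefore open.

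2. **Is there a lock before allocation is disclosed?** Section 5.1 freezes the control plan after approval, but does not say that approval comes before allocation. For the initial plan in the experimental arm it states no approval step. No section supplies the missing link.

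3. **Is the planner masked?** Section 3.1 gives observer blinding only. No section masks the staff who contour or plan.

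4. **Is there discretion at the shared step?** Yes for beam number and directions, and for the control optimisation strategy. For the target it is narrow: the GTV is delineated on imaging signal under one rule, with fixed margins of 1 cm to CTV and 3 mm to PTV (section 5.2).

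5. **Does the re-plan rule close the gap?** No. Keeping the beam directions ties a re-plan to that patient's own initial plan. It does not make initial plans comparable between arms.

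6. **Does central review close the gap?** Only in part. Section 9.1 reviews target volumes and beam arrangement for every experimental plan, but only for the first three control plans. With 60 patients planned per group, that is 60 of 60 against 3 of 60 (3/60 = 5%). If the three are meant per centre, which the text does not say, two centres give 6 of 60 (10%).

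7. **Does the endpoint depend on these choices?** Yes. Under section 7.1.1 the GTV and the 80% isodose bound the region in which a lesion counts. The synopsis words the region differently and also admits lesions adjacent to the high-dose volume, but it too relies on the tumour volume and the high-dose volume. Contour and plan can therefore affect which lesions are eligible to count, as well as lesion risk.

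There is no figure to reproduce. The timing of allocation does not enter the sample size of 120 or the one-sided alpha of 0.025. The protocol contains nothing from which the size or sign of a bias could be calculated.

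**The case against.** The strongest reply is that the protocol contains no error of order. A reader might infer from the baseline tick that randomisation precedes contours and the initial plan. The documents do not support this. The table has no planning column, and its only pre-RT MRI tick is at baseline, while section 5.1 wants the planning MRI within 4 weeks before radiotherapy. If these are the same scan, the baseline column may span the planning period. That part of the objection stands, and the point is limited accordingly.

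The reply also lists safeguards:
- common target and dose rules with fixed margins;
- central review of every experimental plan;
- a dummy run at each centre (section 9.2);
- no model feedback on a control patient's plan until it is approved;
- two independent radiologists.

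These have weight. The common contour rule in particular makes beam choice, rather than the target, the main exposure. But none of them keeps the arm from the person making the initial plan, and the plan review is unequal between arms.

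It can fairly be added that open optimisation in the control arm reflects local standard practice (section 5) and defines the comparator. That is accepted. The freedom is not the defect; exercising it with knowledge of the arm is the risk. Nor can the matter be left to the SAP, since no later analysis restores an initial plan made without knowledge of allocation.

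**Conclusion.** The point holds as an open safeguard. Randomisation is scheduled at the baseline visit, planners are unmasked and have discretion over beams, and nothing requires contours and the initial plan to be approved before allocation is disclosed. Arm-aware initial planning is therefore possible; the protocol does not show that it occurs.

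This rests on two readings. The first is that the initial plan in the experimental arm is made under the same conventional planning rules as the control plan, which section 5.1 implies but does not spell out. The second is that allocation reaches the planning team once it is made, since nothing says that it is withheld.

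The size and direction of any bias are unknown. Any percentage shift in the lesion rate would be an arbitrary assumption, so none is offered. The trial remains randomised, with its sample size and error rates as stated. This is an inexpensive improvement worth making, not a flaw that invalidates the design.

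**What to change.** State one sequence for both arms in section 12.4.1, and show it in both visit tables as a step between the baseline visit and the start of RT:

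1. consent and eligibility;
2. contours and the initial conventional plan approved and locked;
3. allocation requested from the web system;
4. re-planning where allocated;
5. first fraction.

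Section 5.1 should refer to this sequence. Central review of the locked initial plans on the same basis in both arms would complete the protection, but it is a separate and larger effort.

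The main change is wording plus a later call to the randomisation tool. The cost is practical: re-planning, and the central review of the re-plan before first irradiation, cannot be scheduled until allocation is known, so the window before RT is shorter. There is one knock-on effect to check. The 12-month minimum observation rule in sections 2.1, 11 and 12.3.2 counts from randomisation, so its start would move later by the planning interval. The 24-month endpoint window counts from PRT and would not change.
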